## 6. GENERAL CONSIDERATIONS

### 6.1. REFERENCE START DATE AND STUDY DAY

Study Day will be calculated from the reference start date and will be used to show start/stop day of assessments and events.

Reference start date is defined as the surgical procedure day (Day 1 is the day of surgical procedure) and will appear in every listing where an assessment date or event date appears.

- If the date of the event is on or after the reference date then:

Study Day = (date of event – reference date) + 1.

- If the date of the event is prior to the reference date then:

Study Day = (date of event – reference date).

In the situation where the event date is partial or missing, Study Day, and any corresponding durations will appear partial or missing in the listings.

## **6.2. STATISTICAL TESTS**

For the primary efficacy endpoint, for which two treatment group comparisons are performed as described in detail in section 13.1.1, the overall family-wise error rate is controlled at 0.025 level using the Holm's multiple comparisons procedure; confidence intervals will be 95% and all tests will be two-sided, unless otherwise specified in the description of the analyses.

## **6.3. COMMON CALCULATIONS**

The statistical analysis of the data obtained from this study will be performed using SAS® version 9.2 or higher.

All continuous variables will be summarized by number of subjects, mean, standard deviation, median, minimum and maximum. All categorical data will be summarized by frequencies and associated percentages.

## **7. STATISTICAL CONSIDERATIONS**

### **7.1. MISSING DATA**

All study endpoints will be analyzed using the available data. Missing data for efficacy and safety endpoints will not be imputed.

## **8. OUTPUT PRESENTATIONS**

The output module document provided with this SAP describe the manner in which data from this study will be presented and the format and content of the summary tables, figures and listings to be provided by [REDACTED].

## **9. DISPOSITION AND WITHDRAWALS**

All subjects who provide informed consent will be accounted for in this study.

Subject disposition and withdrawals, and protocol deviations, including inclusion and exclusion criteria, will be presented.

Protocol deviations will be summarized for Safety Set, including PD content and PD grading.

Subject disposition will be summarized with counts and percentages for each treatment group and in total. Categories summarized will include the number of subjects who signed informed consent, number of screen failures (with reasons), and the number enrolled, completed, and discontinued, as well as reasons for discontinuation. The summary of disposition will also include the number and percentage of subjects included in each analysis set.

## **10. DEMOGRAPHIC AND OTHER BASELINE CHARACTERISTICS**

Demographic data and other baseline characteristics will be presented will be summarized descriptively as described in section 6.3 for the Safety Set.

No statistical testing will be carried out for demographic or other baseline characteristics.

The following demographic and other baseline characteristics will be summarized for this study:

- age (years) (age = date of signing informed consent - date of birth, rounded down),
- gender,

- ethnicity,
- height,
- weight,
- baseline EQ-5D-5L.

In addition, descriptive statistics for the Safety analysis set will be provided for, at a minimum, the following additional baseline characteristics: medical/surgical history, concomitant medications, and various laboratory data.

Surgery information such as procedure duration and OR time will also be summarized descriptively.

## **11. PRIOR MEDICAL /SURGICAL HISTORY**

A pre-existing condition is one that is present at the start of the study and is to be reported as part of the subject's medical history. It must be reported as a new Adverse Event if the intensity, frequency, or the character of the condition worsens during the study treatment.

Relevant information in this section will be presented to the Safety set and described separately by treatment group.

MedDRA code will be used to summarize the medical/surgical history according to System Organ classification (SOC) and Preferred Term (PT).

## **12. CONCOMITANT MEDICATIONS**

Medications will be presented for the Safety Set.

Concomitant medications used within the period from 7 days prior to the signing of ICF to the end of the study will be documented, excluding medications for surgical anesthesia.

## **13. EFFICACY OUTCOMES**

### **13.1. PRIMARY EFFICACY ENDPOINT**

The primary efficacy endpoint is defined as the proportion of subjects achieving Grade A healing (success) of surgical incision in each group.

#### **13.1.1. SAMPLE SIZE CALCULATION**

One hundred fifty (150) evaluable subjects per study arm will achieve 80% power to detect a non-inferiority margin difference in group proportions of -0.05 for each of the two comparisons using a Pearson Chi-square test with a one-sided significance level of 0.0125. The proportion of successes in the Control group is assumed to be 0.98. The proportion of successes in Test group [REDACTED] or [REDACTED] is assumed to be 0.93 under the null hypothesis of inferiority, presented in section 13.1.2. The power was computed for the case when the actual proportion of successes in the Test group is 0.98.

To account for a potential 10% dropout rate, approximately 167 subjects per arm will be enrolled, for a total of approximately 501 subjects.

#### **13.1.2. PRIMARY ANALYSIS OF PRIMARY EFFICACY VARIABLE(S)**

This is a non-inferiority trial with two treatment group comparisons, [REDACTED] versus control group, and [REDACTED] versus control group. The overall family-wise error rate is controlled at 0.025 level

using the Holm's multiple comparisons procedure. The expected proportion of successes is 0.98 for all the three groups.

For each of the two comparisons, the statistical hypotheses for testing the non-inferiority of the investigational group to control are presented as follows:

$H_0: P_T - P_C \leq -0.05$  tested against the alternative hypothesis

$H_a: P_T - P_C > -0.05$ .

$P_C$  is the proportion of successes (Grade A healing) in the control group and  $P_T$  is the proportion of successes in each of the investigational groups (1 and 2). The proportion of subjects with Grade A healing will be summarized for each treatment group and will be calculated as the number of subjects with Grade A healing divided by the total number of subjects randomized to that treatment who had the surgical wound closed using the randomized suture. Within-treatment group, two-sided 95% confidence intervals for the proportions of successes will be provided using the Clopper-Pearson method.

For the primary endpoint analysis, the Holm's step-down procedure will be used. For each of the two group comparisons, the p-value associated with the non-inferiority test will be calculated using the Normal approximation Z (pooled) statistic. If the smaller p-value is smaller than 0.0125, then the null hypothesis associated with this p-value will be rejected and it will be concluded that the associated Test product is non-inferior to Control; subsequently, the larger p-value will be compared to 0.025 in order to test the non-inferiority of the other Test product to Control. If the smaller p-value is larger than 0.0125, then neither of the null hypotheses can be rejected and it will be concluded that, for both investigational devices, the study failed to demonstrate non-inferiority to Control.

The primary endpoint will be analyzed using the Full Analysis Set (FAS) and Per-Protocol (PP) sets. The PP analysis will be considered the primary analysis, while the FAS analysis will be considered supportive.

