Surgeons should consider the *in vivo* performance when selecting a device for use in patients. The use of this device may be inappropriate in elderly, malnourished or debilitated patients, or in patients suffering from conditions which may delay wound healing.

As with any foreign matter, prolonged contact of any device with salt solutions, such as those found in the urinary or biliary tracts may result in calculus formation. As an absorbable device, ██████████ may act transiently as a foreign matter. Acceptable surgical practice should be followed for the management of contaminated or infected wounds.

As this is an absorbable device material, the use of supplemental nonabsorbable sutures should be considered by the surgeon in the closure of the sites which may undergo expansion, stretching or distention or which may require additional support.

The safety and efficacy of the ██████████ Device have not been established for use in fascial closures (including abdominal wall, thoracic and extremity fascial closures), gastrointestinal anastomoses, cardiovascular tissue, neural tissue, osseous tissue, tendinous tissue, ophthalmic surgery or for use in microsurgery.

Do not re-sterilize/reuse. Reuse of this device (or portions of this device) may create a risk of product degradation, which may result in device failure and/or contamination, which may lead to infection or transmission of blood-borne pathogens to patients and users. Discard open packages and unused devices. Discard packaging that is damaged or opened. Do not use after expiration date.

Precautions

The ██████████ Device contains a loop end and barbs to anchor tissues and does not require knots to secure the device. Tying of knots on the barbed section of the device will damage the

barbs and potentially reduce their efficacy. For the device to function properly, the ██████████

██████████ Device must first be anchored in robust tissue using the fixation loop. Then subsequently engage the barbs into the tissue in a standard closure pattern. When completing placement of the barbed segment in subcuticular tissue, take at least one additional pass in the reverse direction to lock the ██████████ Device in place. In all other tissue layers, take at least two passes in the reverse direction to lock the ██████████ Device in place.

Avoid contacting the ██████████ Device with other materials (e.g., surgical gauze, drapes, etc.) in the surgical field to prevent ensnaring on the barbs.

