Randomization will occur if the patient meets all inclusion criteria and does not meet any exclusion criteria.

The central randomization system will be used in this study, so that subjects will not know their treatment group allocation. Each subject will be randomized to one of the three treatment groups according to the allocation ratio of 1:1:1, and the only difference between the investigational groups and control group lies in the suture material. Each group will include approximately 167 subjects.

3) Visit 3-Surgery

The following information must be obtained during the surgical procedure:

- Surgical data, including:

- Use: Including the code and quantity of study product used, and tissue layer at which the study product is used;
- Suturing time: It is defined as the time required from the first needle insertion for stitching ribbon muscles to the completion of intradermal suture (min);
- Length of operation: It is defined as the time from the incision of skin to the closure of skin (min);
- Total operating room time: It is defined as the time from the start of anesthesia on the subject to the time of leaving the operating room (min);
- Intraoperative suture performance indicators (using VAS scale, see Annex 4-2, collected data of the second case using ██████████ and ██████████ from each Investigator): Ease to pass through tissues, surgical operation profile (including surgical handfeel), suture memory, and wear resistance of suture;
- Concomitant medications: Excluded intraoperative medications for anesthesia;
- Concomitant treatment;
- AEs;
- Product complaints.

Surgical procedures

a. Open thyroid surgical procedure via the anterior cervical curved incision (Kocher's incision):

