- Imaging data of incision: 1 picture of complete neck anterior view containing full length of the incision;
- Wound healing grade assessment: Assessed by Central Imaging evaluators according to the imaging data;
- Postoperative incision pain score;
- EQ-5D-5L;
- Incision SSI, and ASEPSIS score assessed in subjects with confirmed SSI;
- Wound complication assessment, including: incisional wound separation or incisional wound dehiscence requiring intervention, delayed incisional wound healing, etc.;
- Discharge date;
- AEs;
- Product complaints.

5) Visit 5 – Day 28-35 post-surgery

The following information must be obtained at this visit:

- Concomitant medications;
- Concomitant treatment;
- Imaging data of incision: Collect 5 pictures of incision (including a picture of complete neck anterior view containing full length of the incision, a picture taken parallel to the incision plane, a picture taken at a 45° angle to incision plane, and incision lateral view pictures of both sides (one for each));
- Modified Hollander Wound Evaluation Scale;
- Postoperative incision pain score;
- EQ-5D-5L;
- Incision SSI, and ASEPSIS score assessed in -subjects with confirmed SSI;
- Wound complication assessment, including: incisional wound separation or incisional wound dehiscence requiring intervention, delayed incisional wound healing, etc.;
- AEs;
- Product complaints.

6) Withdraw visit – For subjects randomized but without any of study sutures used and for subjects who withdraw ICF

For subjects who are randomized but without any of study sutures used for incision closure, this visit is conducted as early as possible. For subjects who withdraw ICF, this visit is conducted as early as possible with subjects' permission. Telephone visit is acceptable. The following information must be obtained at this visit: AEs; Product complaints.

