8.1 Statistical Design, Method and Analysis Procedure

This study is a multicenter, prospective, randomized controlled study to evaluate the of ██████████ and ██████████ used in thyroid surgery to suture surgical incision. Prior to surgery subjects will be randomized to the investigational group 1 (██████████), investigational group 2 (██████████) or the control group according to the allocation ratio of 1:1:1. The primary **efficacy** endpoint is the proportion of subjects achieving Grade A wound healing (success) of surgical incision in each group. A blind assessment will be performed on the wound healing status by independent Central Imaging evaluators on Day 5-7 post-surgery using the imaging data (a picture of complete neck anterior view, covering full length of the incision).

This is a non-inferiority trial with two treatment group comparisons, investigational group 1 versus control group, and investigational group 2 versus control group. The overall family-wise error rate is controlled at 0.025 level using the Holm's multiple comparisons procedure. The expected success rate is 98% for all the three groups.

For each of the two comparisons, the statistical hypotheses for testing the non-inferiority of the investigational group to control is presented as follows:

- $H_0: P_T - P_C \leq -0.05$ tested against the alternative hypothesis
- $H_a: P_T - P_C > -0.05$

P_C is the proportion of successes (Grade A healing) in the control group and P_T is the proportion of successes in each of the investigational groups (1 and 2).

The proportion of subjects with Grade A healing will be summarized for each treatment group and will be calculated as the number of subjects with Grade A healing divided by the total number of subjects randomized to that treatment who had the surgical wound closed using the randomized suture. Within-treatment group, two-sided 95% confidence intervals for the proportions of successes will be provided using the Clopper-Pearson method.

For the primary endpoint analysis, the Holm's step-down procedure will be used. For each of

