8.8 Selection Criteria and Reason of Subjects Included in the Analysis

All subjects that meet the inclusion/exclusion criteria are considered to meet the requirements for recruitment.

Three analysis sets in the study are defined for this study, as follows:

- FAS consists of all the enrolled subjects who were randomized and for whom the randomized suture materials were used for incision closure.
- PP (evaluable) Set contains all the subjects in the FAS who have no major protocol

deviation, have data available for primary efficacy endpoint and do not meet any of the following criteria:

- Subject undergoes any of the following procedures, in addition to thyroidectomy:
 - 1、 Any surgical procedure which require additional neck incisions or extend the original incision;
 - 2、 Cervical lymph node dissection (except the dissection of lymph nodes in the VI area);
 - 3、 Other unplanned surgical procedures (except the procedure that the investigator doesn't think it will affect the original incision's healing)
- Subject's intraoperative frozen pathology or postoperative paraffin section pathology suggests anaplastic thyroid cancer;
- Subject receives any surgical procedures that lead to re-opening of the cervical incision during the period from the wound closure to the completion of study, except for surgeries related to surgical incision complication or study device.
- Safety Set contains all the enrolled subjects who receive surgery.

Major protocol deviations are deviations that have an impact on the primary endpoint assessment or randomization. These will be determined prior to database lock.

The analysis of primary efficacy endpoint will be performed using FAS and PP Sets. However, while the primary analysis is based on the PP Set, FAS analysis will only be used as supplemental analysis.

The secondary efficacy endpoints will be analyzed using the FAS, while the safety endpoints will be analyzed using the Safety Set.

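### The success rate is conditioned on closure with the randomised suture, the SAP contradicts itself on that condition, and a closure that is started with the assigned suture and then replaced or supplemented is nowhere classified

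*SAP*

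**What the plan says.** **Denominator.** SAP 13.1.2 states that the proportion "will be calculated as the number of subjects with Grade A healing divided by" a count restricted by closure: "the total number of subjects randomized to that treatment who had the surgical wound closed using the randomized suture". Protocol 8.1 has the same condition: "who had the surgical wound closed using the randomized suture". The numerator carries no suture condition of its own.

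**Analysis sets.** Protocol 8.8 builds the condition into the set: "FAS consists of all the enrolled subjects who were randomized and for whom the randomized suture materials were used for incision closure". SAP 5.1 does not; it asks only for randomisation and a post-baseline effectiveness evaluation. In both documents the PP set is a subset of the FAS without major deviations and with primary endpoint data. PP is primary and FAS supportive.

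**Follow-up.** Protocol 7.2.3 provides a withdraw visit, which collects only adverse events and product complaints: "For subjects who are randomized but without any of study sutures used for incision closure, this visit is conducted as early as possible".

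**Closure rules.** Protocol 7.2.3 requires closure with the sutures of the assigned group. The device warnings in 7.2.2 add that "the use of supplemental nonabsorbable sutures should be considered by the surgeon in the closure of the sites", for sites that may expand, stretch or distend or need extra support.

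**Recording.** The Visit 3 item on suture use reads "Including the code and quantity of study product used, and tissue layer at which the study product is used". Footnote e of the schedule in 7.2.1 also lists intraoperative use of suture devices. Neither asks expressly for a non-assigned suture or for the reason it was used.

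**The concern.** Protocol 4.3 says the trial is to show that the barbs do no harm to safety or efficacy. A strand that breaks, does not anchor or does not hold is a failure of the suture during closure, and so belongs to that question. Yet whether the wound was closed with the randomised suture is known only after randomisation, and it depends on a surgeon who, under Protocol 7.1.3, cannot be blinded. No rule makes such an event count in the primary endpoint, and missing data are not imputed.

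The documents also leave open what happens to a mixed closure. Closure has three layers. Protocol 7.2.3 names the study device at the ribbon muscles in group 1 and at the intradermal layer in group 2. The condition does not say whether the assigned suture must complete its layer or only have been used. The choice would fall to case-by-case review. With a 5-point margin and an expected 98% success rate, a few subjects can decide the result: one subject in 150 is 0.67 percentage points.

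**Working it through.** **1. The passages side by side, for a subject whose assigned suture was attempted and then replaced or supplemented**

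| Text | Consequence |
|---|---|
| Protocol 8.1, SAP 13.1.2 (closed with the randomised suture) | Out, if completion is required; in, if some use is enough |
| Protocol 8.8 FAS ("for whom the randomized suture materials were used for incision closure") | In if some use is enough; not defined by layer |
| SAP 5.1 FAS | In, if evaluated after baseline |
| PP set | Depends on whether the change is judged a major deviation |
| Withdraw visit | Applies only if no study suture at all was used for closure; otherwise Visits 4 and 5 and the photograph continue |

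Read literally, a converted wound with Grade A healing could even enter the numerator without entering the denominator.

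**2. The plan's own figure**

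Inputs (Protocol 8.2.1, SAP 13.1.1): success 0.98 in both arms, margin 0.05, one-sided alpha 0.0125, power 80%.

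n = (2.2414 + 0.8416)² × 2 × 0.98 × 0.02 / 0.05² = 149.04, so 150 per arm. Power at 150 is 80.3% by the normal approximation and 80.4% by exact enumeration. 150 / 0.9 = 166.7, so 167 per arm and 501 in all. The stated sample size reproduces.

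**3. Three treatments of a conversion**

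Assumptions: a fraction c of one test arm is converted and none of the control arm; 98% Grade A otherwise; 150 per arm before exclusions. The documents give no value for c.

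Test: Z = (pT − pC + 0.05) / √[p̄(1 − p̄)(1/nT + 1/nC)], rejecting when Z > 2.2414 (the first Holm step), with exact binomial enumeration.

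- Excluded: nT = 150(1 − c), rounded; pT = 0.98.
- Kept and graded from the photograph: nT = 150; pT = 0.98.
- Kept and counted as failures: nT = 150; pT = 0.98(1 − c).

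| c | pT if counted as failures | P(NI) excluded | P(NI) graded | P(NI) counted as failures |
|---|---|---|---|---|
| 1% | 0.970 | 0.773 | 0.804 | 0.535 |
| 2% | 0.960 | 0.776 | 0.804 | 0.298 |
| 3% | 0.951 | 0.780 | 0.804 | 0.145 |
| 5% | 0.931 | 0.794 | 0.804 | 0.025 |

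Counted as failures, the whole margin is used when 0.98(1 − c) = 0.93, that is at c = 5.1%.

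**4. A worked result, control 147/150**

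- Two conversions excluded: 145/148, Z = 0.0497/0.0163 = 3.06, p = 0.0011.
- Two counted as failures: 145/150, Z = 0.0367/0.0186 = 1.97, p = 0.0244. This misses 0.0125. It would pass only as the second Holm step, at 0.025, if the other comparison had already succeeded.
- Three excluded: 144/147, p = 0.0012. Three counted as failures: 144/150, p = 0.064, which fails at either step.

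**5. Conversions in both arms**

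If conversions are equally frequent in the test and control arms and counted as failures, there is no device difference, but the success rate falls in both arms. Power drops from 0.80 to 0.43 at 3% and to 0.31 at 5%.

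**The case against.** A reader might infer that any barbed closure that fails in surgery and is finished with another suture leaves both numerator and denominator and never counts against the device. The documents do not support that. Mixed closures are undefined, not clearly excluded. The protocol FAS asks that the assigned materials were used, not that they completed every layer. The SAP FAS has no suture condition. The numerator has none either. The withdraw visit is limited to subjects with no study suture used, so a partly barbed closure keeps its Day 5-7 photograph. Product complaints, intraoperative adverse events and suturing time are reported descriptively, and device-related re-openings after closure stay in the PP set.

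The sharp fall in power comes from the scoring, not from the denominator. Grade A is a photographic healing grade. If converted wounds are kept and graded at 98%, the chance of success is about the same as if they are excluded. Counting conversion as failure creates a composite endpoint. As a primary rule it would change the estimand, cost power if conversions occur in all arms, and let an unblinded judgement of cause into a blinded endpoint.

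The supplemental-suture text is general device labelling with a qualifier about the site. Use of a non-assigned suture would be a reportable deviation, and set membership is agreed before unblinding.

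All of this stands, and it limits the point. It does not remove the conflict between SAP 5.1 and 13.1.2, supply a rule for mixed closures, or give a suture failure during closure any place in the non-inferiority decision.

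**Conclusion.** The point holds as a gap and a contradiction. The success rate depends on a post-randomisation condition in unblinded hands, the SAP applies that condition in one section and omits it in another, and replaced or supplemented closures have no stated classification.

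The size depends on an unknown. For assumed conversion rates of 1% to 5% in one test arm and none in control, the chance of declaring non-inferiority stays at 0.77-0.79 with exclusion and about 0.80 with photographic grading, but falls from 0.54 to 0.025 if conversions count as failures. If conversions are absent, nothing changes.

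The documents do not establish that the rule always favours the barbed devices, or that scoring conversion as failure is the only correct primary analysis. The PP analysis can remain primary, provided the supportive analysis is freed of the conditioning and the alternative scoring is shown. Severity: should fix.

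**What to change.** 1. Reconcile SAP 5.1 with SAP 13.1.2 and Protocol 8.1 and 8.8, so that the FAS and its denominator include every randomised subject in whom the assigned suture was opened and attempted, whether or not it completed the closure.
2. Keep all such subjects on the Visit 4 and Visit 5 schedule, so that the Day 5-7 photograph exists. Reserve the withdraw visit for subjects in whom no assigned suture was attempted and for those who withdraw consent.
3. Record at Visit 3 any non-assigned suture, its layer and the reason, and tabulate conversions by arm.
4. Pre-specify an FAS sensitivity analysis that scores suture-related replacement or supplementation as not Grade A in all three arms, next to the FAS analysis that grades these wounds from the photograph. Require the report to discuss the non-inferiority conclusion if the two differ.
5. Reconcile the supplemental-suture warning in Protocol 7.2.2 with the assigned-suture rule in 7.2.3. Which text should prevail is for the sponsor and investigators to settle.

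The cost is wording in both documents, a small addition to the Visit 3 form, one table and one analysis. The supportive success rates may be slightly less favourable, and the sensitivity analysis loses power if conversions occur in all arms. The planned sample size and the primary test need not change.
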